4.1.2 Patient Follow Up Survey

The follow up surveys will either be mailed to the participant, along with a return envelope, provided electronically and/or by text message via REDCap survey link, or completed via phone or Zoom call with a staff member, according to patient preference. For patients who opt to complete their follow-up surveys via phone or Zoom call, study staff will not assist them in selecting the correct answers for questions pertaining to their understanding of cancer and genetics. Study staff will follow-up with patients once a week within 2–3-week window to encourage completion of the survey. We will attempt to contact non-responders up to five times to encourage survey participation.

Understanding of personal genomic knowledge will be assessed through an adapted version of a measure created by Freedman and colleagues¹, which evaluated women's knowledge of their personal cancer ER and HER2 status using a two-item question (3 response options; yes/no/I don't know). Our adapted questions will evaluate patients' recall of genomic testing results and the implications of their results (i.e., harmful and unknown). Patient recall will be assessed at all survey timepoints (i.e., at baseline, 10 days, 3 months and 9-months following results disclosure with a clinician).

Engagement in care will be assessed by a novel item that queries patients as to whether WES prompted questions to care providers (yes, no, don't know). We will use items adapted for our CSERII study to ask patients if they recall changes to their cancer treatment as a result of their genomic test results. We will also assess engagement via interactive functionality of HOPE-Genomics (see below). Seeking and sharing information about genetic tests will be assessed using two items from the Health Information National Trends Survey (HINTS) 4 that were adapted for our CSERII study.⁷

Satisfaction with physician/patient communication around the results of gene testing will be assessed with a 7-item measure adapted from HINTS 3 & 4. Satisfaction with care will be assessed using a single item measure from Charles and colleagues that was created to evaluate satisfaction with genetic counseling and that was adapted for our CSER1 study.¹⁴ We have also included two novel questions to assess whether patients (1) recalled asking their healthcare providers about their genetic test results and (2) recalled receiving a copy of their genetic test report.

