4.4 Results Disclosure

We expect results to be available within ~3-14 days of sample acquisition. We will monitor the patients' laboratory data to see when results have been finalized. Lab results and variant interpretations for the HOPE Genomics intervention will be stored in a custom genomic database designed by COH Research Informatics. All results will be validated by study staff before data are input into the HOPE-Genomics tool. All clinicians will receive results through the EHR. Additionally, clinicians with patients in the intervention arm will also be able to view their patients' results through the HOPE-Genomics after individual-level patient data have been entered into HOPE-Genomics. Results will be available to patients in the HOPE-Genomics app approximately 3-14 days after they are available in the EHR.

At this time, we will ask patients in the Return of Results Only intervention arm, (Arm 2) and the Return of Results + Pre-Test Education arm (Arm 3) to log into the HOPE-Genomics tool on their own time. Study staff will provide patients with instructions to create an account and log into the tool using dual-factor authentication. Study staff will track patients' tool access through Google Analytics and call or send automated RedCap reminders to encourage tool use, if necessary. Study staff will track patients' tool access through Google Analytics and call and/or send automated REDCap reminders to encourage tool use, if necessary. In addition, the study staff will be available to help patients access HOPE-Genomics at subsequent clinic/infusion visits or via secure web conference at any point in time following the disclosure of their test results until the end of the study (with coordination with the study team).

Patients in the control arm (Arm 1) will have their results returned in clinic by their provider, with no changes to the clinician's typical delivery method. Patients will be provided an educational pamphlet that generally describes sequencing and will granted access to the HOPE-Genomics tool with their results after completing all follow-up study surveys, approximately 9 months after their results are in the EHR.

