4.5 Follow up Surveys

4.5.1 10-Day Follow-Up Survey

All patients enrolled in the study will be asked to complete a follow-up survey approximately 10 days after results are released in the EHR. The survey will either be mailed to the participant, provided electronically and/or by text message via REDCap survey link or completed over a scheduled phone or Zoom call with a staff member, according to patient preference. If the survey is mailed, the patient will be provided with a return envelope. Follow-up survey reminders will be similar to those outlined for the baseline survey. The follow-up survey outcomes are detailed in Table 1. For participants of both intervention arms, the survey will also include questions about the usability of HOPE-Genomics. Survey measures will be similar to measures detailed in Section 4.1.1.

Patients in Arm 1 (usual care) will receive a modified survey that does not contain questions that pertain specifically to the HOPE-Genomics tool, like usability.

4.5.2 3 Month Follow-Up Survey

Delivery of the follow-up survey and study materials will follow similar procedures mentioned in Section 4.3.1. The 3 Month follow-up survey outcomes are detailed in Table 1. Survey measures will be similar to measures detailed in Section 4.1.1.

4.5.3 9 Month Follow-Up Survey

Delivery of the follow-up survey and study materials will follow similar procedures mentioned in Section 4.4.1. The 9 Month follow-up survey outcomes are detailed in Table 1. Survey measures will be similar to measures detailed in Section 4.1.1. Participants in the Usual Care Arm will view their results in the HOPE-Genomics tool after completing the 39Month Follow-Up Survey. None of their follow-up surveys will contain questions pertaining to the HOPE-Genomics tool or its usability.

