6.2.1 Primary Outcome

In Aim 1, recall rates of personal genomic results at the 10-day post-disclosure timepoint for Arms 2 and 3 of the study will be pooled together so that the main comparison is a two-sample test of proportions between patients under usual care (Arm 1) vs. patients with any exposure to the HOPE-Genomics tool (Arms 2/3). Pilot studies indicate that a recall rate for patients with an actionable somatic finding are approximately 39% under usual care. An analytical sample of 390, assuming a 39% recall rate under usual care (Arm 1: n = 130) with a 15% improvement using the tool (Arms 2/3: n = 260), will be sufficient to detect a difference in proportions with 80% power and alpha = 0.05 (two-sided with no adjustment for multiplicity). Rates of recall will be analyzed using a two group Chi-Square test of equal proportions, and logistic regression when controlling for covariates such as age and education level. The overall fit of the model will be examined using Hosmer-Lemeshow goodness-of-fit test and ROC curves. If any normality issues arise, non-parametric techniques such as the Mann-Whitney test will be deployed. Recall rates will be defined as the number of participants who correctly recall somatic test results, which will be assessed in the second question of the 10-day post-disclosure survey.

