Appendix K: Follow-Up Survey Invitation Letter (10 day/3 month/9 month for Intervention Arms)

Dear [PATIENT NAME],

This is the HOPE-Genomics team at City of Hope. You may remember speaking with [consenter] recently about your participation in the HOPE-Genomics study. Thank you for viewing your genomic test results in the HOPE-Genomics tool for patients at City of Hope!

To help us make this tool the best it can be, we would love to hear your thoughts. There will be 3 follow-up surveys, approximately 10 days, 3 months, & 9 months after receiving your genomic test results. This is the [SURVEY NAME]. This survey will ask you about cancer, genetics, and what you understand about your genetic testing results and cancer. The survey may also ask you about your experience viewing your test results in the HOPE-Genomics tool. Some of the questions may look familiar from an earlier survey. We would like you to complete this survey as well.

[For REDCap]. You can access the [SURVEY NAME] online by using this link: [LINK]. Please complete the survey, using the provided study ID: [INSERT STUDY ID].

[PAPER ONLY]. Please complete the attached survey and mail it back to us in the enclosed self-addressed return envelope.

After completing this survey, you will be provided with a [INSERT 5/\$10] gift card as a thank you for your time and feedback.

Participation in this study will not involve any treatment. The study is confidential and your responses to survey questions will not be passed along to your medical provider or anyone outside of the study team.

If you have any questions about this research study, please call [CONSENTER'S NAME] at [INSERT CONSENTER'S PHONE NUMBER], or the Principal Investigator, [name] at [contact] or the Clinical Research Coordinator, [name] at [contact]. You can also reach the Institutional Review Board at City of Hope by calling [contact].

Thank you so much,

The HOPE-Genomics Team

[name], [name], [name], [name], and [name]

Division of Clinical Cancer Genomics

Medical Oncology and Therapeutics Research

Department of Population Sciences

City of Hope Comprehensive Cancer Center

[name]

[name]

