Appendix P: HOPE-Genomics Survey Script (Via Phone or Zoom)

Hello, my name is [CRA NAME] and I am a clinical research assistant with the HOPE-Genomics Team at City of Hope. Is there a [([name]) PATIENT NAME] here?

Hi [([name]) PATIENT NAME], I am reaching out to you today because you recently expressed an interest in completing your [INSERT SURVEY NAME] over [PHONE/ZOOM]. Is now still a good time to meet?

[IF NO: schedule another time to talk to patient]

[IF YES] Wonderful. Before we begin, I would like to mention a few points about the survey. We estimate that this will take approximately [INSERT TIME VALUE] to complete together.

The purpose of this survey is to get your feedback about your cancer care at City of Hope and what you understand about genomics. I am going to read the survey verbatim and record all the responses you provide. These responses will be kept confidential and identified only by a number. Please keep in mind that you are free to not answer any question in this survey, for any reason. As we go through the survey, please let me know if you have any questions or need clarification. This survey does include general questions about genetics and cancer. For these questions, please keep in mind that I cannot assist you selecting the correct answers.

Do you have any questions before we begin?

[AFTER ANSWERING ANY QUESTIONS]: Proceed to read IRB-approved survey verbatim.

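### A looked-up answer would count as recall in the primary endpoint, and looking it up is easier in the two tool arms

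*Combined protocol and SAP*

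**What the plan says.** **Endpoint.** Section 6.2.1: "Recall rates will be defined as the number of participants who correctly recall somatic test results". The item is the second question of the 10-day survey. No condition is attached about answering without the result at hand.

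**Survey mode.** Section 4.5.1 offers paper and electronic completion, "The survey will either be mailed to the participant, provided electronically and/or by text message via REDCap survey link", and continues "or completed over a scheduled phone or Zoom call with a staff member, according to patient preference".

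**Access to the result.** Section 4.4 asks Arms 2 and 3 "to log into the HOPE-Genomics tool on their own time", with reminders, and offers staff help with access "at any point in time following the disclosure of their test results until the end of the study". Sections 4.3 and 4.4 give Arm 1 the tool only after its last survey, at about 9 months.

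**Timing.** Section 4.4 puts results in the tool about 3-14 days after the EHR. Section 4.5.1 puts the survey about 10 days after EHR release. Appendix H says the survey will follow viewing of the tool, and Appendix K thanks intervention patients for having viewed their results there.

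**Safeguard.** Section 4.1.2, for phone or Zoom completion: "study staff will not assist them in selecting the correct answers for questions pertaining to their understanding of cancer and genetics". Appendix P, after mentioning general questions on genetics and cancer: "For these questions, please keep in mind that I cannot assist you selecting the correct answers". The Appendix K letter gives the link ("You can access the [SURVEY NAME] online by using this link") and does not ask for answers from memory; nor do Appendices L and R.

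**The concern.** Aim 1 is about knowledge, measured as recall. If a patient opens the result while answering, the answer is scored as correct recall, and nothing in the plan would separate the two. That matters little if look-up is equally common in all arms. Here it need not be: the tool is part of the randomised intervention, patients are reminded to open it near the time of the survey, and it runs on a phone (Section 4.2), which may be the device that receives the survey link. Any excess look-up in Arms 2 and 3 pushes the primary comparison towards the tool. A positive result could then partly mean that tool patients could open their result while answering. Look-up that is not recorded at the time cannot be reliably reconstructed afterwards.

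**Working it through.** **Inputs from Section 6.2.1:** Arm 1 recall p1 = 0.39 with n1 = 130; Arms 2/3 planned at p2 = 0.54 with n2 = 260; two-sided alpha 0.05; 80% power.

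**Step 1: the plan's own figure.** Pooled rate = (130 × 0.39 + 260 × 0.54)/390 = 0.49. Null SE = √[0.49 × 0.51 × (1/130 + 1/260)] = 0.0537. Alternative SE = √[0.39 × 0.61/130 + 0.54 × 0.46/260] = 0.0528. Power = Φ[(0.15 − 1.96 × 0.0537)/0.0528] = Φ(0.85) ≈ 0.80. The stated 80% reproduces. No figure in the plan is wrong on this point; the issue is what the endpoint measures.

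**Step 2: a look-up model (assumed).** Let true recall be 0.39 in every arm, so the tool has no effect. Let f be the share of Arm 2/3 non-recallers who look the answer up and get it right, net of look-up in Arm 1. Then observed Arm 2/3 recall = 0.39 + 0.61f. The documents give no value for f, so a range is shown. The probability is exact binomial enumeration of the chi-square test (130 vs 260), counting only rejections that favour the tool.

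| f | Observed Arm 2/3 recall | Probability of wrongly favouring the tool |
|---|---|---|
| 0 | 39.0% | 2.5% |
| 5% | 42.1% | 8.3% |
| 10% | 45.1% | 20.5% |
| 20% | 51.2% | 62% |

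Break-even: f = 0.15/0.61 = 24.6% would by itself produce the whole planned 15-point difference.

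**Step 3: look-up in Arm 1 as well.** If 10% of Arm 1 non-recallers look up and 20% in Arms 2/3 do, the observed rates are 0.39 + 0.061 = 45.1% and 0.39 + 0.122 = 51.2%, and the probability is about 20%. With equal look-up in all arms it returns to the nominal level.

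**Step 4: the lag before results reach the tool.** If availability were uniform over days 3 to 14 (assumed) and everyone answered on day 10, (10 − 3)/(14 − 3) = 64% of Arm 2/3 patients would have something to look up. Replacing f by 0.64f lowers the 8%, 21% and 62% to about 6%, 11% and 30%.

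**The case against.** Several points on the other side stand.

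- **The survey form is not in the text available for review.** It is the natural place for a from-memory instruction. Section 6.0 says an amended survey will be submitted before use. Silence in letters and scripts does not show that the form is silent.
- **Supervision varies.** A reader might infer that the item is always answered unsupervised. Section 4.5.1 also offers phone and Zoom, although those modes do not stop a patient from consulting a source.
- **The tool is not the only source.** A reader might infer that only Arms 2 and 3 can look up. Arm 1 receives results from the clinician, and the follow-up survey in Section 4.1.2 asks about having received a copy of the report.
- **Opening the tool takes effort.** Section 4.2 requires a password and a code sent to the phone, and the session expires after 30 minutes without use.
- **Some patients may have no result in the tool on day 10,** as in Step 4. Against this, Appendices H and K place the survey after viewing, and the 2-3 week reminder window in Section 4.1.2 lets answers come later.
- **Motive is weak.** The measure from which the items are adapted offers a don't-know response, and the gift cards reward completion, not correctness. Not every look-up would yield a correct answer.

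The strongest reading, that patients do look up and that this would account for a positive result, is not supported. The documents show only that look-up is possible, easier in the tool arms, and neither discouraged nor recorded in any visible text.

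**Conclusion.** The point holds as a gap in how the primary endpoint is protected. Following the visible plan, a look-up is scored as recall, access is easier in Arms 2 and 3, and the resulting bias would favour the tool. Its size is unknown. The probabilities of about 8%, 21% and 62% rest on assumed net look-up of 5%, 10% and 20%, no true effect, 39% recall in every arm and 130 versus 260 analysed; they fall where results are not yet in the tool. The 24.6% figure is a break-even, not an estimate. This is a cheap improvement to make, not a demonstrated flaw in the comparison. If the survey form already carries a from-memory line, that part of the concern falls away and the items on recording, analysis and Appendix P remain.

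**What to change.** 1. Unless the survey form already has it, put one identical line before the recall items in all arms and all modes, including Appendix P: answer from memory, without opening a report, a portal or the HOPE-Genomics tool.
2. Right after the recall question, add one yes/no item in all arms asking whether the patient looked at their results while answering.
3. In Appendix P, extend the no-assistance sentence to questions about the patient's own results.
4. In Section 6.2.1, add a sensitivity analysis of the primary comparison that counts self-reported look-up as not recalled, by the same rule in every arm.

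Do not recode answers because a tool login overlaps the survey; at most, report overlap descriptively. Only Arms 2 and 3 can have a login, so the rule could penalise only them. It could also catch patients who open the tool for the usability questions in the same survey. Mailed surveys have no REDCap completion time, and Section 4.3 describes the analytics data as anonymised. If 10% of correct Arm 2/3 answers were recoded under the planned effect, 54% would become 0.9 × 54% = 48.6%, and power would fall from 80% to about 43%.

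Cost: a wording amendment, one extra item and one sensitivity analysis. Observed recall may be somewhat lower, and some look-up will still go unreported.

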4.6 Medical Record Abstraction

Throughout the study, study staff will perform a limited medical record abstraction of consented participants. Primary outcome data will include high-risk screening, surgery, chemoprevention, targeted therapies, genetic counseling, informing family members, and cascade testing. Covariate data will include sociodemographic information, cancer information, germline and somatic genomic biomarker testing, and dates and types of treatments for cancer. Additional outcomes are detailed in Table 1.

5.0 DATA AND SAFETY MONITORING AND UNANTICIPATED PROBLEMS

5.1 Definition of Risk Level

This is a low risk study, as defined in the [City of Hope Institutional Data and Safety Monitoring Plan \(DSMP\)](#), because it involves minimal risk, as the risks of harm anticipated are not greater than those ordinarily encountered during daily life or during the performance of routine psychological tests in a

healthy person. This study involves the administration of surveys before and after an educational intervention, which will be integrated into the patient's usual course of clinical care. The study Principal Investigator is responsible for monitoring protocol conduct and reporting all reportable events to the City of Hope (COH) Data and Safety Monitoring Committee (DSMC) and Institutional Review Board (IRB) in accordance with the City of Hope Institutional Deviation policy, [and Clinical Research Adverse Event and Unanticipated Problem policy](#).

5.2 Unanticipated Problems (UP) Involving Risks to Subjects or Others

An unanticipated problem is any incident, experience or outcome that meets all three of the following criteria:

- Unexpected (in terms of nature, severity, or frequency) given the following: a) the research procedures that are described in the protocol-related documents such as the IRB approved research protocol, informed consent document or Investigator Brochure (IB); and b) the characteristics of the subject population being studied; **AND**
- Related or possibly related to participation in the research (possibly related means there is a reasonable possibility that the incident, experience, or outcomes may have been caused by the procedures involved in the research); **AND**
- Suggests that the research places participants or others at greater risk of harm (including physical, psychological, economic, or social harm) than previously known or recognized.

Any UP that occurs during the study conduct will be reported to the DSMC and IRB in accordance with the [City of Hope's Institutional policy](#) using the electronic submission system, [iRIS](#).

6.0 DATA ANALYSIS

As noted in Section 4.0, we are administering the survey items in order to help with item reduction for the trial. We will generate descriptive statistics (e.g., distributions, means) in order to evaluate for ceiling and floor effects. An amended survey will be submitted prior to administration.

Primary outcome (i.e., patient knowledge, recall rates) will be assessed at the 10-day post-disclosure timepoint.

We will be using MRA and survey data to evaluate if participants received contextual guideline-concordant care. This will involve review of receipt of prophylactic surgery, chemoprevention, targeted therapy for germline mutations, consultation with genetic counseling/ genetic specialists, informing family members, and family member cascade testing. To generate concordance scores for patients already on active therapy, patients will be asked about their current and/or planned cancer treatment at baseline and at each follow-up timepoint in the study (i.e., chemotherapy, radiation therapy, cancer-directed surgery, hormone therapy, immunotherapy, and targeted therapy). Patients will be considered as being contextually guideline-concordant if they receive at least 75% of the recommended guidelines. In sensitivity analyses, we will vary the cutoff for guideline- concordance between 50% and 100%. Survey data will also be used to evaluate usability of the HOPE-Genomics application, the psychosocial impact of using the tool, engagement in care, genetic knowledge, and understanding of genomic test results

6.1 Sample Size and Accrual Rate:

We plan to anchor our cohort on patients with somatic testing. We expect to accrue 465 patients: 155 per each arm. We assume that there will be a 10% attrition rate among accrued patients, leaving us with a final analytical sample of 390 patients. For the first 3 months, we assume that 17 patients are enrolled each month, during which time we will evaluate and optimize study processes. After this we will increase monthly accrual to 35 patients. We expect to be complete with accrual in 16 months. Patient participation will be approximately 7 months consisting of baseline pre-testing followed by genetic testing/results disclosure and then post-testing. The estimated total study time including analysis will be 26 months.

6.2 Statistical Analysis Plan:

The study data will consist of three main areas:

- 1) patient knowledge testing and clinical care recommendations via survey-based questions
- 2) patient demographic information collected via the electronic medical record (EMR); and
- 3) patient clinical and treatment information collected via the EMR.

This information will be used to evaluate outcomes, predictors and adjust for covariates.

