3.0 PARTICIPANT NUMBER, RECRUITMENT, COHORT CHARACTERISTICS AND ELIGIBILITY

3.1. Participant Number

We anticipate recruitment and enrollment of approximately 465 patients for this study and assume a 10% overall attrition rate after enrollment. We will recruit from among patients who consent to the COH IRB 07047 Precision Medicine protocol and who have been or had been diagnosed with cancer. For 07047 overall, we estimate approximately 4000 total patients in year 1 of Precision Medicine (beginning CY 2021), 6000 total patients in year 2, and larger numbers yet in subsequent years, demonstrating likely feasibility. Given that patients who consent to 07047 may receive WES (e.g. GEM ExTra), Panel

Testing (e.g. HopeSeq), and/or germline (e.g. Invitae) as part of their care, they will have the genomic testing that is necessary for this education intervention study.

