3.4. Cohort Characteristics and Eligibility

3.4.1 Patient Participants

Patients will be eligible if: 1) they are enrolled in COH IRB 07047, 2) have a cancer diagnosis, 3) they are having somatic, germline or paired somatic/germline sequencing, 4) they are fluent in English, 5) they have an ECOG performance status of 0-2, and 6) they are ≥ 18 years old.

Patients will be ineligible if they 1) are unable to provide informed consent.

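### Ten per cent attrition from 465 leaves about 418 patients, not the stated 390, which implies about 16%; the 80% power at 390 is correct

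*Combined protocol and SAP*

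**What the plan says.** On numbers, section 6.1 states "We expect to accrue 465 patients: 155 per each arm", and then "We assume that there will be a 10% attrition rate among accrued patients, leaving us with a final analytical sample of 390 patients". Section 3.1 gives the same enrolment and says the plan will "assume a 10% overall attrition rate after enrollment". Section 6.2.1 carries 390 into the power statement: "An analytical sample of 390, assuming a 39% recall rate under usual care (Arm 1: n = 130"), against 260 in Arms 2 and 3 combined, for a 15% improvement, 80% power and two-sided alpha of 0.05.

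On who is analysed, section 3.4.1 accepts patients if "they are having somatic, germline or paired somatic/germline sequencing". Section 4.5.1 says: "All patients enrolled in the study will be asked to complete a follow-up survey approximately 10 days after results are released in the EHR". Section 6.2.1 defines the primary outcome by somatic results: "Recall rates will be defined as the number of participants who correctly recall somatic test results". The nearest thing to a link between eligibility and outcome is one sentence in section 6.1: "We plan to anchor our cohort on patients with somatic testing". The 39% control rate in 6.2.1 comes from pilot patients who had an actionable somatic finding.

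**The concern.** The attrition rate, the number enrolled and the number analysed are tied by one multiplication, and the three stated values do not satisfy it. The 10% appears in two sections, so it is not an isolated misprint. No second loss is described that would bring 418 down to 390. What is at stake is the retention target against which conduct will be judged: losing 16% of patients would miss a 10% assumption but would still deliver the 390 that the power statement needs.

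The second matter is the denominator of the primary comparison. A patient who has only germline sequencing has no somatic result to recall, yet is eligible and receives the 10-day survey. The text does not say whether such a patient is left out, counted as not recalling, or handled in some other way. If that is decided after the data are seen, the primary result depends on the decision.

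**Working it through.** **Inputs.** From 6.1: 465 enrolled, 155 per arm, 10% attrition, 390 analysed. From 3.1: 465 and 10%. From 6.2.1: 39% control rate, 15% improvement, 130 against 260, two-sided alpha 0.05, 80% power.

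**1. The plan's power figure.** Read the 15% as percentage points, so p1 = 0.39 and p2 = 0.54. With pooled variance under the null,

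power = Φ{ [ (p2 − p1) − 1.96 √( p̄(1 − p̄)(1/n1 + 1/n2) ) ] / √( p1(1 − p1)/n1 + p2(1 − p2)/n2 ) }.

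- p̄ = (130 × 0.39 + 260 × 0.54)/390 = 0.49.
- Null standard error: √(0.2499 × 3/260) = 0.0537; times 1.96 = 0.1052.
- Alternative standard error: √(0.2379/130 + 0.2484/260) = 0.0528.
- (0.15 − 0.1052)/0.0528 = 0.848, and Φ(0.848) = **80.2%**.

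The smallest sample for 80% power at this ratio is 130 + 260 = 390, exactly the plan's number. Reading the 15% as a relative gain (39% to 44.85%) gives only 19.3%, so percentage points is the reading the plan used.

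**2. The attrition step.**

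- Forward: 465 × 0.90 = **418.5**; per arm 155 × 0.90 = 139.5.
- Implied by the stated sample: 1 − 390/465 = **16.1%**; per arm 1 − 130/155 = 16.1%.
- Backward at 10%: 390/0.90 = 433.3, so 434. The shortcut 390 × 1.10 gives 429. Neither is 465.
- Backward at 16%: 390/0.84 = 464.3, so 465.

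The 465 and the 390 therefore fit each other at 16%, and the 10% is the value that does not fit.

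**3. Power if 10% is the true assumption.** With 139.5 against 279, the null standard error is √(0.2499 × 3/279) = 0.0518, and times 1.96 it is 0.1016. The alternative standard error is √(0.2379/139.5 + 0.2484/279) = 0.0509. Then (0.15 − 0.1016)/0.0509 = 0.950, and Φ(0.950) = **82.9%**.

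**4. Could an unstated second loss explain it?** From 418.5 to 390 is 28.5 patients, and 28.5/418.5 = 6.8% of completers. Ten per cent attrition followed by 6.8% not evaluable for somatic recall would close the gap. The documents do not say this.

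**5. The analysis set.** This part involves no plan figure to reproduce. Side by side: 3.4.1 admits germline-only patients; 4.5.1 surveys everyone enrolled; 6.1 describes the 390 as accrued patients less attrition; 6.2.1 scores somatic recall. The sentence in 6.1 about anchoring the cohort expresses an intention, and the criteria in 3.4.1 do not apply it. It sets no eligibility limit, analysis set or scoring rule.

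**The case against.** The strongest reply to the arithmetic point is that it changes nothing of substance. Section 6.2.1 fixes 390 analysed and 80% power, and that is right. The error runs in the safe direction, and neither enrolment nor the test is affected. This stands. A reader might infer that the planned power is uncertain between 80% and 83%, or that 465 is the wrong enrolment. The documents support neither: the power statement is explicit, and 465 follows from 390 at 16% attrition.

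On the analysis set, the reply is that 6.1 and 6.2.1 both signal a somatic population. The survey item that measures recall is also not in the available text, and it may deal with patients who had no somatic test, for example by letting them correctly report that they have no such result. That limits the point to the protocol's wording, but it does not supply the missing rule.

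A reader might also infer that the trial is underpowered because of germline-only patients. For assumed shares of 5% to 20%, excluding them gives 78.1% to 70.8% power from a base of 390, or 80.9% to 73.9% from a base of 418. Counting them as not recalling gives 76.2% to 63.2%, or 79.1% to 66.4%. These figures only show that the choice matters. The documents give no share, the base depends on how the attrition figure is resolved, and such patients may already be inside the planned loss.

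**Conclusion.** The attrition statement is wrong as written. Ten per cent of 465 leaves about 418, and 390 corresponds to 16.1%, a discrepancy of about 28 patients. The direction is conservative. The 80% power for 130 against 260 is correct (80.2%), given 39% against 54% and the 15% read as percentage points. What needs reconciling is the attrition figure that links enrolment to the analysed number.

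The absence of a stated primary analysis set is a secondary clarification. It rests on the protocol text alone, without sight of the survey item, and no loss of power is demonstrated. A related limit should be stated with it: the 39% comes from a narrower group than everyone with somatic testing, so any power quoted for the wider group assumes that the same control rate applies there.

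**What to change.** In sections 3.1 and 6.1, state one consistent set of figures, with enrolment unchanged at 465:

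- about 16% attrition, 390 analysed, 80% power; or
- 10% attrition, about 418 analysed, about 83% power, with the sample and arm sizes in 6.2.1 updated to match.

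If the difference between 418 and 390 is an allowance for patients not evaluable for somatic recall, say so and give it as a separate line (about 6.8% of completers).

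In section 6.2.1, add that the primary comparison is made among randomised patients for whom somatic or paired sequencing was ordered at enrolment, with the same rule in every arm. Section 4.1 places randomisation immediately after enrolment, so the test ordered is a basis that later results cannot influence. Add a note that the 39% comes from patients with an actionable somatic finding, a narrower group than this set.

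The cost is wording in three sections, with no change to enrolment, eligibility or data collection. If the set so defined is expected to be smaller than 390, the restated power will fall below 80% and the plan should report it.
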